#### **Duration of treatment**: will depend on HCV-genotype

- 24 weeks for genotypes 2 and 3
- 48 weeks for genotypes 1, 4 and 5

For patients, who do not show an adequate response at week 12 (adequate response at week 12 = drop of HCV RNA of at least 2log or HCV RNA-negativity), treatment can be stopped and the patient enters follow up phase.

**Duration of study:** Will include the treatment period (24 or 48 weeks) as well as the follow-up period of 24 weeks (totally: 48 or 72 weeks)

### 10.3. Treatment Group B Patients:

Patients will receive one week of treatment with PegIntron and Rebetol, followed by a combination treatment with PegIntron, Rebetol, AdoMet and betaine. The dosages are identical to group A.

### 10.4. Dose Modification (for both group A and group B):

Dose modifications should be done as outlined in section 12.2.1.

## 11. Study Visits and Evaluations:

Appendix 1 defines the planned study visits and evaluations.

Unscheduled visits may be performed if required for assessment of laboratory parameters or clinical safety. An unscheduled visit must be performed within one week of the last visit for patients who have a hemoglobin decrease more than 2 g/dl since the entry visit or decreased to below 10 g/dl. At this new visit, a hematology sample should be obtained for analysis and, if the hemoglobin value still meets the above criteria, the dose reduction/discontinuation and additional monitoring visits will apply.

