#### 12.2.1 Management of Adverse Events

Subjects having AEs will be monitored with relevant clinical assessments and laboratory tests, as determined by the investigator. The investigator is expected to report ongoing AEs at completion of the clinical study to the primary care physician who will determine the need for and provide standard medical care.

Any actions taken and follow-up results must be recorded either on the appropriate page of the CRF or in a follow-up letter to ESSEX Chemie AG as well as in the subject's source documentation. Follow-up laboratory results should be filed with the subject's source documentation.

For all AEs that require the subject to be discontinued from the study, relevant clinical assessments and laboratory tests will be repeated on at least a monthly basis until final resolution or stabilization of the event(s).

Adverse events can be managed by dose reduction of one or both study medications. In the case of life-threatening AEs as described in Section 12.2.4 both PEG-Intron plus REBETOL must be discontinued permanently.

Reduced doses will be achieved by decreasing the injection volume of the PEG-Intron and the number of capsules/tablets of REBETOL as referenced in Table 1 and Table 2. While at a reduced dose level, the subject should return for assessment at a minimum of every two weeks until the AE resolves or the subject is stable. If the AE persists but does not fall into the range for permanent discontinuation, the reduced dose of PEG-Intron and/or ribavirin (whichever has been reduced) may be continued. At the discretion of the investigator, the dose of PEG-Intron and/or ribavirin may be increased to full dose, directly or in steps, when the AE subsides. If the AE recurs, the subject should be maintained at the previously tolerated reduced dose or, at the discretion of the investigator, discontinue treatment.

Table 1 Dose Reduction for REBETOL

Screening Weight a	Full Daily Dose	First Reduced Dose	First Reduced Number of Capsules	Second Reduced Dose	Second Reduced Number of Capsules
40-65 kg	800 mg/day	600 mg/day	1 in AM/2 in PM	400 mg/day	1 in AM/1 in PM
>65-85 kg	1000 mg/day	800 mg/day	2 in AM/2 in PM	600 mg/day	1 in AM/2 in PM
>85-105 kg	1200 mg/day	1000 mg/day	2 in AM/3 in PM	800 mg/day	2 in AM/2 in PM
>106-125 kg	1400 mg/day	1000 mg/day	2 in AM/3 in PM	800 mg/day	2 in AM/2 in PM

a: Use standard rounding procedures: for 0.1-0.4 kg, round down and 0.5-0.9 kg, round up.

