#### 12.2.2 Management of Selected Hematologic and Biochemical Parameters

Based on the side effect profile of pegylated interferon alfa and ribavirin there are selected hematologic and biochemical parameters (listed in Table 3) that have specific requirements for dose reduction or permanent discontinuation of therapy. All other hematologic and biochemical parameters will be managed using the Grades 1-4 guidelines in Appendix 2.

Table 3 Dose Reduction for Selected Hematologic and Biochemical Parameters

	Dose Reduction (see Table 1-2)	Permanent Discontinuation of Treatment PEG- Intron and REBETOL
Hemoglobin	<10 g/dL (Rebetol) a	<8.5 g/dL
White Blood Count	<1.5 x 10  /L (PEG-Intron) a	<1.0 x 10  /L
Neutrophil Count	<0.75 x 10  /L (PEG-Intron) a	<0.5 x 10  /L
Platelet Count	<50 x 10  /L (PEG-Intron) a	<25 x 10  /L
Bilirubin – Direct		2.5 x upper limit of normal
Bilirubin – Indirect	>5 mg/dL (>85.5 μmol/L) (Rebetol) a	>4 mg/dL (>68.4 μmol/L) (for >4 weeks)
Creatinine		>2.0 mg/dL (>176.8 μmol/L)
ALT/AST		2 x baseline and >10 x upper limit of normal

a: Study medication to be reduced.

If a subject meets the criteria for dose reduction, apply the first dose reduction level. An additional visit and blood sample analysis will be scheduled. If the first dose reduction does not improve the hematologic or biochemical results, a second dose reduction will apply.

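### Protocol sections 11 and 12.2.2 (Table 3) disagree on whether a first or a repeat haemoglobin value triggers ribavirin reduction or permanent discontinuation

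*Protocol*

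**What the plan says.** **Section 11 (Study Visits and Evaluations).** The rule is specific to haemoglobin: "An unscheduled visit must be performed within one week of the last visit for patients who have a hemoglobin decrease more than 2 g/dl". The fall is counted from entry, and a value under 10 g/dl is the alternative trigger. A new sample is taken at that visit, and "if the hemoglobin value still meets the above criteria, the dose reduction/discontinuation and additional monitoring visits will apply". The order is measure, repeat, act, and discontinuation is named among the actions that follow the repeat.

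**Section 12.2.2 and Table 3.** The haemoglobin entry for dose reduction is "<10 g/dL (Rebetol"), and the entry for permanent discontinuation of both PEG-Intron and Rebetol is below 8.5 g/dL. The text under the table applies to all its parameters: "If a subject meets the criteria for dose reduction, apply the first dose reduction level". Next comes "An additional visit and blood sample analysis will be scheduled", and then "If the first dose reduction does not improve the hematologic or biochemical results, a second dose reduction will apply". The order is measure, reduce, recheck. No repeat sample is mentioned for the discontinuation column.

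**Links between them.** Neither section refers to the other. Section 10.4 sends the reader to section 12.2.1 for dose modification and does not mention section 11.

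**The concern.** Both sections cover a haemoglobin value below 10 g/dl, so the issue arises at a threshold they share and is not a matter of different cut-offs. They place the repeat sample on different sides of the action. Every value below 8.5 g/dL is also below 10 g/dl, so section 11 covers the stop level as well.

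Patient safety and consistent conduct are at stake. Two investigators who each follow a written instruction could handle the same haemoglobin course differently, and at the stop level one patient could be permanently off both drugs while the other continues on a reduced dose. A monitor would also have no fixed standard for calling either course a deviation.

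**Working it through.** The protocol gives no figure to reproduce. The check applies each rule to the same haemoglobin course.

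**Inputs**
- Section 11: trigger is below 10 g/dl or a fall of more than 2 g/dl since entry; repeat visit within 7 days of the last visit.
- Table 3: reduction (Rebetol) below 10 g/dL; permanent discontinuation below 8.5 g/dL.
- Section 12.2.1, "Table 1 Dose Reduction for REBETOL", full / first reduced / second reduced dose in mg/day: 800/600/400 (40-65 kg), 1000/800/600 (>65-85 kg), 1200/1000/800 (>85-105 kg), 1400/1000/800 (>106-125 kg).

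**Stop level, first value 8.4 g/dL**

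| Repeat value | Section 11 | Table 3 |
|---|---|---|
| Still below 8.5 | Discontinuation after the repeat, up to 7 days later | Permanent discontinuation; no repeat mentioned |
| 8.5 to below 10 (e.g. 9.0) | Criteria still met; judged on the repeat value, this is the reduction range | Permanent discontinuation; no repeat mentioned |
| 10 or above, fall of no more than 2 g/dl | Criteria no longer met; the text attaches no action | Permanent discontinuation; no repeat mentioned |

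In the second and third rows the two texts can lead to different outcomes, not just different dates. In the first row, the most extra ribavirin in the >65-85 kg band is 7 × 1000 = 7000 mg if the full dose continues until a repeat on day 7. One further weekly PegIntron injection might also fall in that interval.

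**Reduction level, first value 9.8 g/dL: dose until the recheck**

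If section 11 is followed, the dose stays full until the repeat. If section 12.2.2 is followed on the first value, the first reduced dose applies.
- 40-65 kg: 800 − 600 = 200 mg/day
- >65-85 kg: 1000 − 800 = 200 mg/day
- >85-105 kg: 1200 − 1000 = 200 mg/day
- >106-125 kg: 1400 − 1000 = 400 mg/day

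Over at most 7 days this is 7 × 200 = 1400 mg, or 7 × 400 = 2800 mg in the heaviest band. The 400 mg/day figure uses Table 1's full dose of 1400 mg. Section 10.2 lists 1200 mg for all patients above 85 kg, and with that dose the gap would again be 1200 − 1000 = 200 mg/day.

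**Reduction level: dose after the recheck**

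The result depends on whether the two rechecks are the same visit.
- *Same visit, value not improved:* section 11 gives the first reduced dose and section 12.2.2 the second. The pairs are 600 vs 400, 800 vs 600, 1000 vs 800 and 1000 vs 800, a gap of 200 mg/day in every band.
- *Separate visits* (section 11's repeat comes before the first reduction, section 12.2.2's recheck after it): both give the first reduced dose after the repeat, and no lasting one-level gap follows from the text.

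**The case against.** The strongest defence is that the sections run in sequence. Section 11 sets no dose levels, so it must rely on rules stated elsewhere. It is specific to haemoglobin, whereas section 12.2.2 covers every parameter in Table 3. On this reading a low haemoglobin is confirmed first and section 12.2.2 starts after that. The additional monitoring visits in section 11 would then be the recheck in section 12.2.2.

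Much of this stands. Section 11 says that action applies if the repeat still qualifies; it does not say only if. Section 12.2.2 gives an order but no time limit and no number of measurements, so acting at once is an inference, and its recheck is undated. A reader might infer that the sections are strict opposites, so that obeying one always breaches the other. At the reduction level the text does not go that far, because the sequential reading is available.

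The defence does not remove the problem. No text states the sequence, section 12.2.2 speaks of meeting the criteria and not of confirming them, and section 10.4 bypasses section 11. Section 11's criteria include a fall of more than 2 g/dl, which Table 3 lacks, so section 11 is not simply a confirmation step for Table 3. At the stop level, the sequential reading would make a value that Table 3 lists for permanent discontinuation wait for a repeat sample, and Table 3 mentions none.

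A reader might also infer that section 11 obliges full dosing to continue at 8.4 g/dl. It does not: sections 9 and 9.1 let the investigator interrupt or end treatment for the patient's welfare, and section 12.2.4 requires permanent discontinuation for a life-threatening event. These provisions limit the harm but do not settle which haemoglobin rule governs.

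**Conclusion.** Wrong as written: an internal contradiction over whether a first or a repeat haemoglobin value triggers action.

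- **Stop level, the clearest conflict.** A first value below 8.5 followed by 8.5 to below 10 g/dL means permanent discontinuation under Table 3 but possibly only a reduction under section 11. This assumes that section 11's action is judged on the repeat value, which the text does not spell out. Where both lead to a stop, the delay of up to 7 days is an upper bound.
- **Reduction level.** The ribavirin dose until the recheck may differ by 200 mg/day, or 400 mg/day in Table 1's heaviest band. This assumes that section 12.2.2 is followed on the first value.

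Two further inferences are not supported. A lasting dose difference of one level arises only if section 11's repeat and section 12.2.2's recheck are taken to be the same visit, which the protocol does not say. An effect on the sustained virologic response rate cannot be quantified either, since nothing in the protocol links these dose differences to response. The case rests on patient safety and on having a rule that can be followed consistently.

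**What to change.** Reconcile section 11 with section 12.2.2 and Table 3. In one place, state:

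1. for the reduction level, whether a first or a confirmed haemoglobin value triggers action;
2. separately, the same for the permanent-discontinuation level, including what applies when the repeat value falls in a different range from the first;
3. whether the recheck counts towards the first or the second reduction step, and whether the section 11 repeat and the section 12.2.2 recheck are one visit or two.

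The other section should then refer to that text, and section 10.4 should point to it too. The choice of rule is for the clinical team.

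The cost is one amended paragraph and the cross-references. No new kind of visit is needed, because the protocol already provides for both the repeat sample and the later monitoring visits.

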## 12. Adverse Events and Safety

An adverse event is any untoward medical occurrence or unfavorable and unintended sign in a subject administered a pharmaceutical product, biologic (at any dose), or medical device, whether or not considered related to the use of that product. This includes the onset of new illness and the exacerbation of pre-existing conditions.

Additionally, any event that is associated with or observed in conjunction with a product overdose (whether accidental or intentional) or a product abuse and/or withdrawal is also considered an adverse event.

All adverse events must be recorded in the subject's medical records and on the case report form. The onset and end dates, severity and relationship to study drug will be recorded for each adverse event. The severity of the adverse event will be assessed according to specific guidelines (Section 12.1). Any action or outcome (e.g., hospitalization, discontinuation of therapy, etc.) will also be recorded for each adverse event.

Subjects will be questioned and/or examined by the investigator or his/her designee for evidence of adverse events. The questioning of subjects with regard to the possible occurrence of adverse events will be generalized such as, "How have you been feeling since your last visit?" The presence or absence of specific adverse events should not be elicited from subjects.

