#### **Exclusion criteria:**

- Women with ongoing pregnancy or breast feeding.
- Positive test at screening for anti-HAV IgM Ab, HBsAg, anti-HBc IgM Ab, HBe Ag.
- Positive test at screening for HIV.
- History or other evidence of a medical condition associated with chronic liver disease other than HCV (e.g., hemochromatosis, autoimmune hepatitis, alcoholic liver disease, toxin exposures).
- Hypersensitivity to study drugs.
- Participation in any other clinical trial within 30 days of entry into this protocol.
- Treatment with any investigational drug within 30 days of entry into this protocol.

- History or evidence of decompensated liver disease (Child-Pugh B/C) and a Child-Pugh score >5. Ascites, coagulopathy, hyperbilirubinemia, hepatic encephalopathy, or hypoalbuminemia and a Child-Pugh score >5 are conditions consistent with decompensated liver disease.
- History or other evidence of bleeding from esophageal varices or other conditions consistent with decompensated liver disease.
- Hepatocellular carcinoma (HCC) or α-Fetoprotein >50µg/l.
- Patients with organ transplants other than cornea and hair transplant.
- Therapy with any antisystemic or immunmodulatory treatment (including supraphysiologic doses of steroids or radiation) ≤6 months prior the first dose of study drug
- Hemoglobinopathy (e.g. thalassemia) or any other cause of or tendency for hemolysis.
- Any known preexisting medical condition that could interfere with the patient's participation in and completion of the study such as:
- Preexisting psychiatric condition, especially depression, or a history of severe psychiatric disorder, such as major psychosis, suicidal ideation and/or suicidal attempts (based on a mandatory psychiatric advice).
- CNS trauma or active seizure disorders requiring medication.
- Significant cardiovascular dysfunction.
- Poorly controlled diabetes mellitus.
- Renal dysfunction, i.e. serum creatinine levels  $\geq 1.5$  times upper limit of normal.
- Autoimmune diseases.
- Evidence of severe retinopathy (e.g. CMV retinitis, macular degeneration).
- Any medical condition requiring, or likely to require during the course of the study, chronic systemic administration of steroids.
- Clinical gout.
- Important substance abuse (alcohol >80 g/d, i.v. drugs etc.).
- Active opportunistic infections.
- Non-Hodgkin lymphoma or Hodgkin lymphoma.
- Kaposi sarcoma.
- Inability or unwillingness to provide informed consent or abide by the requirements of the study.

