## 9.1 Subject Discontinuation Criteria

Subject's participation may be terminated for any of the following reasons:

- Serious or life-threatening adverse event (AE).
- Failure to comply with the dosing schedule, study procedures, or other study requirements.
- Subject's request (subjects may discontinue treatment at any time for any reason).
- Pregnancy during the study period.
- The investigator feels that it is in the subject's best interest to discontinue treatment at that time.
- Confirmation that the subject meets the protocol's exclusion criteria with regard to history of psychosis, suicidal ideation, or suicide attempts at any time during the study.

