#### 12.2 Monitoring Adverse Events

Subjects having adverse events will be monitored with relevant clinical assessments and laboratory tests, as determined by the investigator. All adverse events must be followed to satisfactory resolution or stabilization of the event(s).

Any actions taken and follow-up results must be recorded either on the appropriate page of the case report form, as well as in the subject's source documentation. Follow-up laboratory results should be filed with the subject's source documentation.

For all adverse events that require the subject to be discontinued from the study, relevant clinical assessments and laboratory tests must be repeated at clinically appropriate intervals until final resolution or stabilization of the event(s).

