#### 12.2.3 Management of Depression During Study

Subjects who develop mild depression may continue their study medication and should be monitored weekly (by visit or by phone) for four to eight weeks. If the subject's status is stable, the subject may resume the normal visit schedule with instructions to call the investigator immediately if the subject feels that the depression has worsened. If the subject's condition worsens, see instructions for moderate and/or severe depression below.

\*\* For patients > 120 kg, use  $80 \mu g/0.5$  ml vial

Subjects with moderate depression should have their dose of PEG-Intron reduced according to Tables 1-2. Subjects are to be monitored weekly (by visit or phone, at least two visits should be in the office) for four to eight weeks (depending on the subject's status) to assure that their status is stable. These subjects may remain on reduced PEG-Intron dosing if the condition is considered stable and does not interfere with the subject's normal activities. Other clinical management intervention may be instituted as necessary. Subjects will be instructed to call the investigator immediately if they feel their depression has worsened. If the subject's symptoms do not improve but are stable for four weeks, the investigator should consider psychiatric consultation. If the subject's condition worsens, the subject should immediately discontinue both drugs and the investigator should make a priority assessment of the severity of the subject's condition. Appropriate psychotherapeutic measures should be instituted and the subject should be followed weekly or biweekly (depending on the investigator's clinical judgment) by visit or by phone until the subject's status has returned to baseline conditions.

A subject with severe depression according to the criteria outlined by the Diagnostic and Statistical Manual of Mental Disorders (DSM-IVTM, Appendix 3) or with suicidal ideation/attempt will discontinue all study medications permanently and will obtain psychiatric consultation immediately by referral to a psychiatrist by the investigator, until depressive symptoms have moderated and improved to baseline conditions. The subject should not resume therapy and should be followed until resolution of the symptoms.

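### Section 12 bars asking about specific adverse events and no mood or suicidality assessment is scheduled, so first detection of the states that trigger 12.2.3 and 9.1 rests on an open question and on observation

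*Protocol*

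**What the plan says.** Section 12 fixes how adverse events are sought. It opens two routes: "Subjects will be questioned and/or examined by the investigator or his/her designee for evidence of adverse events". It then narrows the interview: "The questioning of subjects with regard to the possible occurrence of adverse events will be generalized such as", followed by an example that asks how the patient has been since the previous visit. The paragraph ends: "The presence or absence of specific adverse events should not be elicited from subjects". No class of event is exempted.

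Section 12.2.3 sets actions by grade of depression. At the lowest grade, "Subjects who develop mild depression may continue their study medication and should be monitored weekly". Moderate depression leads to a change in PEG-Intron dosing. Severe depression by DSM-IV criteria (Appendix 3), or suicidal ideation or attempt, leads to permanent discontinuation. Section 9.1 adds, as a reason for which participation may end, confirmation that the subject meets the exclusion criteria on "history of psychosis, suicidal ideation, or suicide attempts at any time during the study".

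At entry, the exclusion for psychiatric history is "based on a mandatory psychiatric advice". Section 11 refers to Appendix 1 for the planned visits and evaluations. Neither Appendix 1a nor 1b has a row for mood, depression or suicidality at any visit.

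**The concern.** New or worsening depression on treatment is an adverse event under Section 12's own definition, which covers new illness and worsening of an existing condition. The rule against eliciting specific events therefore covers it. Two other sections then act on its grade and on suicidal ideation. A site that follows Section 12 to the letter would not open the subject of mood or suicidal thoughts, and nothing in the schedule opens it either.

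What is at stake is how the trial first learns that a patient has reached one of these states. Suicidal ideation without a plan can be present with nothing to see, and mild depression may not emerge in reply to a general question. Staff who see the problem must choose between two instructions in the same protocol, and may choose differently. That would also make the psychiatric event rates hard to interpret.

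**Working it through.** No figure in the plan bears on this and no statistical calculation applies. The check sets the provisions side by side and counts the contacts that the rule governs.

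**1. Triggers that have a scheduled measurement.** The parameters in Table 3 (Section 12.2.2) are blood counts and chemistry values. Both appendices schedule hematology and blood chemistry at baseline, at the regular treatment visits and at follow-up. Pregnancy, a discontinuation criterion in Section 9.1, is tested every 4 weeks on treatment.

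**2. Triggers that do not.** Depression has its own management section, and suicidal ideation is a trigger in both 12.2.3 and 9.1. Neither has a row in Appendix 1a or 1b.

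**3. Contacts governed by the interview rule, 48-week course (Adverse Events row of Appendix 1).**
- Group A: 1 (end of the pretreatment week) + 3 (days 1, 2, 4) + 6 (weeks 1, 2, 4, 6, 8, 12) + 6 (weeks 18, 24, 30, 36, 42, 48) = 16.
- Group B: 6 (weeks 1, 2, 4, 6, 8, 12) + 6 (weeks 18 to 48) = 12. Its adverse-event cell for days 1, 2 and 4 is blank.
- After week 12 routine visits are 6 weeks apart. After treatment there is one visit, at 6 months.

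These counts show where the rule applies. They do not measure lost detection.

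**4. Routes to first detection that remain.**
- The open question, at each of these contacts.
- Examination. Section 12 allows it, and the physical-examination row is ticked wherever the adverse-event row is.
- Observation by others. In Appendix 3, symptom items 1, 2, 5 and 8 accept it. Item 9, which contains suicidal ideation, states no such route.
- Unscheduled visits for clinical safety (Section 11), and events such as a suicide attempt that come to notice by themselves.

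**5. After recognition.** Section 12.2 applies: "Subjects having adverse events will be monitored with relevant clinical assessments and laboratory tests, as determined by the investigator". Section 12.2.3 adds directed follow-up; a patient with mild depression "should be monitored weekly (by visit or by phone) for four to eight weeks" and is told to call if it worsens. Section 12.1 requires every event to be graded. Nothing bars follow-up questions about an event already reported or seen.

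**Result.** The gap is confined to first detection. It is widest for the state with no stated observer route (suicidal ideation) and for the mildest grade of depression.

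**The case against.** The strongest reply is that the documents contain no direct contradiction. Open, non-leading questioning is a deliberate way to collect adverse events. Section 12.2.3 is conditional: it says what to do when depression develops and sets no duty to look for it. Section 9.1 is permissive. Section 12 does not expressly forbid a clinical psychiatric assessment, and its example question could well draw an answer about mood. Grading also refers to Appendix 2, which is not in the text at hand, so its psychiatric content cannot be judged.

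Much of this stands, and it rules out several stronger readings that a reader might infer:

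- *The depression rules can operate only if the patient volunteers the symptom.* Not supported; examination, observation by others and unscheduled visits remain open.
- *A site cannot apply Appendix 3 or assign a grade.* Not supported once an event is recognised, since 12.2 and 12.2.3 then allow directed assessment.
- *Six-weekly visits fall short of the weekly contact in 12.2.3.* This compares routine visits with follow-up that begins only after recognition.
- *The missing row for psychiatric advice at entry shows that the step was dropped.* Weak; the exclusion criteria already make it mandatory, and the schedule omits other eligibility items too, such as the ocular examination.

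What the reply does not answer is that the rule is stated without exception and no scheduled assessment offsets it. Saying that an assessment is not expressly barred still leaves each site to decide which instruction governs.

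**Conclusion.** The point holds as a tension between a stated interview rule and two safety provisions. Followed as written, the plan gives poorer first detection of suicidal ideation and mild depression than it would if these symptoms could be asked about at the same visits. The rule covers 16 on-treatment contacts in group A and 12 in group B over 48 weeks.

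The conclusion rests on two assumptions: that sites read Section 12 literally, and that some patients with these symptoms neither mention them in reply to a general question nor show them. The documents give no rate for either. They therefore do not support a statement that a given share of cases would be missed, or that treatment would be stopped later by a given time. This is a cheap improvement to the protocol, not a flaw that undermines the trial.

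**What to change.** Reconcile Section 12 with Sections 9.1 and 12.2.3:

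- State in Section 12 that the rule against eliciting specific events does not apply to the depressive symptoms and suicidal ideation on which 12.2.3 and 9.1 act.
- Show the matching assessment at existing visits in Appendices 1a and 1b, with method and timing left to the investigators. Appendix 3 should not be named as the screening tool: 12.2.3 applies it only to severe depression, and its criterion D excludes symptoms due to a medication.
- Record on the case report form whether such an event was elicited or volunteered, so that volunteered adverse-event rates stay interpretable.

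The cost is a short addition to visits already planned and one field on the form. The downside is that recorded depression rates will be somewhat higher than by open questioning alone, which the flag makes visible. No dose, grade threshold or stopping rule changes.
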